## 2.2.1 Formative Evaluation Process:

In summary, the formative evaluation will begin by identifying baseline characteristics (i.e., before and/or during the early stages of implementation) of the organization and team that may impact implementation. This will be followed by: 1) assessment of readiness to implement EQUIPPED; 2) monitoring of the implementation process; 3) monitoring of implementation progress; 4) qualitative interviews addressing implementation factors suggested by approximately the 6-8 months following initial implementation of EQUIPPED; and 5) evaluation of program sustainability approximately 1 year after the delivery of the delivery of the first EQUIPPED report.

### **Steps in the Formative Evaluation Process**

- 1. Collection of Baseline Characteristics that may Impact Implementation.** The eight sites will be asked to identify all individuals directly involved in the planning and execution of implementing EQUIPPED (e.g. clinical champions, ED Chiefs, pharmacists CACs). This is termed the core implementation team. Additionally, the eight sites will be asked to identify ED providers and staff that may encounter changed clinical decision-making as a result of implementation of the applications. These sites will be asked to complete a baseline site information document (1 survey report per site/medical center filed via VA REDCap Survey software) that will collect information on core implementation team members and processes and size and composition of the medical centers and impacted clinical services, as well as

identify additional ED providers and staff potentially impacted by the implementation. The research team may update lists of names of individuals or information from the site information document as needed to conduct the study.

2. **Assessment of ORC.** Organizational readiness for change is the extent to which organizational members are prepared as a group to make changes in organizational policies/practices that are necessary to implement and support innovation use (change commitment) and their perceived ability to do so (change efficacy). As with individuals, attributes impacting ORC include change valence (perceived value of the innovation) and information about perceived task demands, resources available, and situational context (e.g., competing demands).

**ORC Survey:** Core implementation team members and ED providers will receive the validated Organization Readiness for Implementing Change measure, a 12-item computer-based survey which examines perceptions of organizational-level change efficacy and commitment to newly implemented interventions. Survey responses will objectively examine ORC as a two-dimensional construct encompassing change commitment and change efficacy. This instrument was developed specifically to measure aspects of the Weiner Theory of ORC. The survey may include additional context questions and will receive IRB approval prior to being fielded. The survey will be fielded via VA REDCap survey software.

**ORC Semi-Structured Qualitative Phone Interview:** In addition, we will conduct semi-structured qualitative telephone interviews of the core implementation team and approximately 3-5 ED providers at each site to assess ORC and factors that are hypothesized to predict ORC (i.e. change valance/value place on the apps and assessment of what it will take to implement the EQUIPPED program). Semi-structured interviews will allow us to study implementation processes, which tend to be non-linear and context sensitive and will permit us to compare patterns across cases. The semi-structured interview guide will need to receive IRB approval interviews are conducted.

3. **Quarterly Documentation of Process/Workflow of Implementation.** As part of the quality improvement support (i.e., not research activity) for implementing EQUIPPED, the QI team will work with each site to establish and summarize the workflow used as part of equipped. Components of the workflow process will then be stored in a Microsoft Excel or Word spreadsheet or document to be sent to the sites for updates approximately every three months. The exact format of the summary, which may be updated and will be retained by the research team, will potentially vary based on the quality improvement needs and decisions of each participating site. .
4. **Bi-monthly Monitoring of Implementation – Implementation Progress.** We will also measure the degree of implementation and barriers and facilitators of implementation process through approximately bi-monthly facility-level reports from the eight sites collected through a computerized survey using the VA REDCap survey software. Site progress with implementation will be assessed using the Stages of Implementation Completion (SIC). The SIC enumerates key pre-implementation, implementation and sustainability milestones. Dates by which specific implementation milestones were reached will be identified. We will then examine if the degree of ORC is associated with the rapidity with which sites go through implementation steps. Bi-monthly (every other month) reports will also include assessment of barriers and facilitators identified through the ORC measurement process.
5. **Evaluation of the Implementation Process – Qualitative Interviews.** At approximately 6-8 months following the start of the implementation process at each of the eight sites, we will

conduct semi-structured qualitative telephone interviews among the core implementation team at each site to assess OTIE factors suggestive of implementation success. The goal will be to interview the same individuals interviewed at baseline. The questions composing the qualitative interview guide will depend upon the formative evaluation. As such, the guide will be developed after the initial implementation of EQUIPPED and approved by the IRB prior to use.

6. **Assessment of Sustainability.** At approximately one-year post-implementation at each site, we will assess the sustainability of EQUIPPED.

Sustainability (PSI) Survey: The Mancini & Marek Model of Community-based Program Sustainability will be used to conceptually guide the evaluation of sustainability. Mancini & Marek propose that six elements are important to achieve long-term sustainability: Leadership competence, effective collaboration, demonstrating program results, strategic funding, staff involvement and integration, and program responsibility. The validated 23-item Program Sustainability Index (PSI) computer-based survey measures the 6 sustainability elements.

Sustainability Semi-Structured Qualitative Phone Interview: Each core implementation team member and ED provider may be surveyed. Additionally, using semi-structured interview methods, we will interview the members of the core implementation team at each site. Precise timing of the interviews may be impacted by individuals' schedules in relation to time of the intervention and previous interviews. We have previously used the combination of PSI and qualitative interviews to evaluate the sustainability of a multi-facility VA program. The questions composing the qualitative interview guide will depend upon the formative evaluation. As such, the guide will be developed after the initial implementation and approved by the IRB prior to use.

7. **Consent Process for Formative Evaluation.** Staff participation in the formative evaluation is entirely voluntary. Some individuals may feel self-conscious or embarrassed if asked questions about something with which they are unfamiliar. Additionally, because research participants are VA employees, they may be concerned their responses will become known to colleagues or supervisors. To minimize this risk, we are requesting a waiver of documented consent, in part, to avoid providing a link between the research participant and the data collected.

An introductory email may be sent from a known individual at each site informing each potentially eligible participant of the study. The introductory email need not be resent upon outreach for subsequent surveys or invitations to participate in interviews with the same participants.

For the surveys, the potential introductory email described above will be followed by a scripted email (must be approved by the IRB) sent from study staff containing information about the study and informed consent. Clicking the link to start the survey implies informed consent.

For the qualitative interviews, the potential introductory email described above will be followed by a scripted email sent from study staff containing information about the study and informed consent. Study staff will follow-up either by email or phone to schedule a phone interview with interested parties. At the start of the scheduled interview, the person conducting the interview will ask if there are any questions about the study and review the elements of informed consent. The study staff member will gather verbal informed consent from the participant(s) prior to proceeding with the interview. Consent documents must be approved by the IRB prior to beginning related study procedures.

## 2.2.2 Formative Data Analysis

The analysis plan described below may be adjusted based on changes in related scientific methods and/or to fit the specific properties of collected data.

Core to the concept of formative evaluation is continual analysis of results and feedback to stakeholders. Like with statistical analysis, the analysis plan laid out below may be adjusted based on the state of the science related to such analysis and the specific features of collected data. Key data sources are qualitative interviews, surveys to assess organizational readiness for change, and collection of detail about organizational characteristics and implementation process and progress. All qualitative interviews will be transcribed in full. Rapid analysis approaches will generate preliminary findings to share among the research team. This effort will involve an initial review of factors identified as directly impacting the process of supporting implementation and impact on clinical workflow. Rapid analysis will be followed by in-depth content analysis. Content analysis to examine the telephone interviews will involve three phases: data coding, within-case analysis, and between-case analysis. In the data coding phase, we will use qualitative data analysis software (ATLAS.ti or other appropriate analysis software) to code the study data. The OTIE will provide a starting list of codes, which we will supplement with emergent codes as analysis proceeds. Using a common codebook, two research staff members will conduct a preliminary test of codes by independently coding approximately five transcripts (more may be independently reviewed if determined to be necessary). Based on the preliminary test, the research staff members will sharpen the coding manual's definitions, decision rules, and examples. Research assistants will code the remaining documents.

In the second phase, we will conduct a within-case analysis of each VA using ATLAS.ti to generate reports of all text segments for each code. We will assess the degree to which the construct emerges in the data (its "strength"), the degree to which the construct positively or negatively affects implementation (its "valence"), and the degree to which relationships among constructs are consistent with the hypothesized model. We will assess support for the hypothesized relationships by using three criteria proposed by Trochim^34 and Miles and Huberman. First, we will look for the overall covariance of the constructs (e.g., whether VA clinics exhibiting strong implementation climate have supportive administration). Second, we will look for explicit attributions or the identification of plausible mechanisms to link the two constructs (e.g., participants attribute a strong implementation climate to the deployment of appropriate implementation policies and practices).

In the third phase, we will apply the same criteria across the cases to determine if cross-case variation in implementation is consistent with the hypothesized relationships in the model. Consistent with the organization-level focus of the model, we will aggregate and analyze quantitative data on implementation policies and practices (e.g. staffing levels) and other study constructs using simple statistics. In addition, we will create within-case and between-case data displays that cross-tabulate the quantitative and qualitative data in order to facilitate the use of pattern-matching logic.

### 2.2.3 Linking Measures Within and Across Implementation Processes from Different Data Sources:

We will combine quantitative measures of the degree of ORC, factors outlined in the OTIE that may influence implementation process, completeness of implementation progress, and sustainability to both implementation and intervention effectiveness outcomes. These data will be supplemented with qualitative data sources such as semi-structured individual interviews and supplemental process information. Inclusion of the qualitative component will enhance understanding of the local context. Quantitative and qualitative findings will produce mixed method findings to inform our understanding of the process of implementing EQUIPPED.

## 2.3 Aim 3. Micro-Costing the Active and Passive Feedback Versions of the EQUIPPED Intervention

Because the earlier version of the EQUIPPED intervention was done as a quality improvement project, we do not have detailed information on how much the intervention costs. For example, while the 10 sites that have implemented a QI version of EQUIPPED received an average of \$50,000 from the Office of Geriatrics and Extended Care, we have no way of knowing details of how that money was spent and whether costs were covered. By micro-costing the intervention we will be able to learn details of specific factors that may impact the cost of the intervention to the organization. Such costs will impact feasibility of wide and sustained implementation of EQUIPPED, if successful. Specific costs will account for 1) labor costs; 2) equipment; and 3) overhead costs such as utilities. The cost of the intervention will be considered from the VA health system perspective, hence, we will not consider individual patient-level direct or indirect costs. Costs will consider both the cost of implementing the program and carrying it out. Because many of the tools have been developed for the intervention and will be provided to the medical centers, the incremental cost of the program will not include the cost of developing these tools.

The micro-costing analysis plan described in this section may be adjusted based on changes in related scientific methods and/or to fit the specific properties of collected data.

Micro-costing of the intervention involves direct measurement of the labor inputs required to both implement and conduct each intervention task. Labor cost includes the fixed costs of implementation planning (e.g., participation in meetings) and training staff of the intervention processes as well as the variable cost of delivering the intervention to each provider. We have developed a log sheet with instructions that can be used by a sample of providers to log their activity time for patients in a given project over the course of a one-week period. The training, implementation, and intervention-related time of each provider will be multiplied by his/her respective wage rate (including fringe benefits), aggregated, and then divided by the number of Veterans served at each ED to derive per-Veteran intervention labor cost for a site. We will account for equipment needed to deliver the interventions (e.g., computers, patient handouts). The VA healthcare system also incurs substantial indirect costs such as administrative costs, utilities, etc., that are not specific to a health service. We will calculate a cost multiplier using the total indirect and direct cost variables in the VA's Managerial Cost Accounting System

(formerly Decision Support System) extract file and apply it to the above direct cost estimates to derive total (direct + indirect) intervention cost.

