be provided to the statistician based at the Birmingham site of the Birmingham/Atlanta GRECC each month for outcome assessment of PIM prescribing. In addition to feedback of individual prescribing patterns, providers also receive anonymous peer benchmarking comparing his/her individual performance to other ED providers at the same site (i.e., a scorecard of PIM prescriptions). This monthly feedback will come in the form of an emailed link to a clinical dashboard showing individual and site level prescribing data for each provider. No patient-identifiable health information will be included in the provider feedback form; however, site champions will have access to individual records if a provider would like to review specific cases to determine the appropriateness of a given prescription.

1.4.2 EQUIPPED with active provider feedback includes the same 3 components as those included previously with the addition of 1:1 in-person provider feedback using academic detailing.

- 1) The initial individual feedback session will be provided in-person to all staff providers (physician, APRN, PA). Clinical pharmacists or an ED provider may partner with the site champion to provide 1:1 feedback depending upon team composition at each site. In-person 1:1 provider feedback typically requires about 15 minutes and involves the following: a) an introduction of the provider's individual report structure and their baseline data as well as the current month's prescribing pattern; b) review the specific drug classes of PIMs that were prescribed during the reporting period; c) comparison of individual prescribing data to the cohort of peer providers within local ED; d) review of the top 5 PIM classes to avoid for the local ED; e) discussion of evidence-based alternative treatments appropriate for older adults; f) a brief demonstration of the EQUIPPED order set appropriate to that provider's needs based on prescribing of PIMs; and g) allowing time for provider question and discussion.
- 2) The onsite EQUIPPED champion will be an ongoing local expertise to provide consultation on clinical questions resulting from the 1:1 sessions such as consideration of appropriate medication alternatives.

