**Stage 3 – Continue Provider Feedback and Measurement of Outcomes for 1 Year:**

- 1) ED providers will receive monthly electronic provider prescribing feedback reports for monthly PIM rates, including the number of older Veterans seen in the ED, number of prescriptions given, and the number of PIMs (including drug class).
- 2) *Active Provider Feedback:* In addition to the electronic feedback reports available for the remote intervention, the champion (or clinical partner) will provide 1:1 academic detailing that includes audit and feedback with peer benchmarking to ED providers and ongoing monthly 1:1 feedback to outlier PIM prescribers in the ED at the site.

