Per standard VA-wide Health Services Research & Development operating procedures for transcribing VA research recordings, approved staff from the VA Salt Lake City (VASLC) will transcribe the EQUIPPED audio files. The VASLC has a Professional Transcription Service available to VA sites and monitored by their own IRB. The EQUIPPED audio recordings to be transcribed by VASLC staff will be labeled by the subject's unique alphanumeric code and saved behind the VA Firewall in EQUIPPED study's secure shared project folder on the Atlanta or Durham VAMC researcher servers. The VASLC transcription staff will be given access to a sub-folder within EQUIPPED study's secure project folder located on the Durham IRB server (study folder labeled EQUIPPED IIR) where audio files are located. While not anticipated, similar arrangements may be made to access data on the Atlanta researcher server if needed. Approved study staff will place a copy of the audio files in this folder for an approved VASLC transcriptionist to access for the purposes of transcription. The VASLC transcriptionist will transcribe each interview verbatim and save the completed transcript in the sub-folder using the same alphanumeric code. No data (audio files, in process transcripts, or completed transcripts) will leave the Durham or Atlanta secure research server. As completed transcripts become available, approved study staff will move these files from the transcription sub-folder into another sub-folder that is only accessible to study staff, where they will be stored and accessed for qualitative analyses.

**Paper records of data:** As referenced in Section 2.3, cost data will be calculated by using a log sheet with instructions that can be used by a sample of providers to log their activity time for patients in a given project over the course of a one-week period. This log sheet will be collected by the Site Champion and sent via encrypted email to study staff. Any hard copy files containing identifiable information will be kept in a locked file cabinet in a locked office space under the care of study research staff.

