In a parallel cluster randomized trial, we will randomize 8 VA facilities to implement EQUIPPED with either passive provider feedback or active provider feedback. Specifically, all sites will implement EQUIPPED components including: didactic education concerning the Beers Criteria; decision support by order sets; and monthly provider prescribing feedback. However, passive provider feedback sites will implement monthly electronic provider feedback via individual prescribing reports using a novel clinical dashboard with audit, feedback and peer benchmarking, while active provider feedback sites will implement one-to-one (1:1) in-person academic detailing that includes in-person audit, feedback, and peer benchmarking and engagement with an on-site champion. In order to inform the eventual dissemination strategy, we will also include formative evaluation and micro-costing of the two methods of implementing provider feedback as part of EQUIPPED. To assess the optimal implementation of EQUIPPED and overall program effectiveness, our specific aims are:

Specific Aim 1 (Primary Aim): To compare the effectiveness of EQUIPPED with in-person academic detailing including proactive feedback (*active feedback*) vs EQUIPPED with passive electronic audit and feedback (*passive feedback*) intervention by comparing the monthly proportion of PIM prescribing as % of individual prescriptions (primary outcome) in each arm. It is hypothesized that the decline in PIM rates will be greater in the presence of EQUIPPED with active feedback compared to EQUIPPED with passive feedback.

Specific Aim 2: Using a formative evaluation approach, we will evaluate the effectiveness of EQUIPPED implementation with passive feedback compared to EQUIPPED implementation with active feedback using including semi-structured qualitative telephone interviews and quantitative survey data.

Specific Aim 3: Using micro-costing methods, we will calculate the difference in the detailed cost of the passive vs. active feedback versions of EQUIPPED.

1. Rationale for the study sample size

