Specific costs will account for 1) labor costs; 2) equipment; 3) and 3) overhead costs such as utilities. The cost of the intervention will be considered from the VA health system perspective, hence, we will not consider individual patient-level direct or indirect costs.²⁶ Costs will consider both the cost of implementing the program

and carrying it out. Because many of the tools have been developed for the intervention and will be provided to the medical centers, the incremental cost of the program will not include the cost of developing these tools.

Micro-costing of the intervention involves direct measurement of the labor inputs required to both implement and conduct each intervention task. Labor cost includes the fixed costs of implementation planning (e.g., participation in meetings) and training staff of the intervention processes as well as the variable cost of delivering the intervention to each provider. We have developed a log sheet with instructions that can be used by a sample of providers to log their activity time for patients in a given project over the course of a one week period. The training, implementation, and intervention-related time of each provider will be multiplied by his/her respective wage rate (including fringe benefits), aggregated, and then divided by the number of Veterans served at each ED to derive per-Veteran intervention labor cost for a site. We will account for equipment needed to deliver the interventions (e.g., computers, patient handouts). The VA healthcare system also incurs substantial indirect costs such as administrative costs, utilities, etc., that are not specific to a health service. We will calculate a cost multiplier using the total indirect and direct cost variables in the VA's Managerial Cost Accounting System (formerly Decision Support System) extract file and apply it to the above direct cost estimates to derive total (direct + indirect) intervention cost.

3. Method of randomization

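### Aim 3 relies on a one-week time log with no stated week, repetition, logger or scaling rule, so intermittent 1:1 detailing may be missed or over-scaled and the active-passive labour difference estimated very imprecisely

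*Protocol*

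**What the plan says.** The target is set out under Specific Aim 3 in the SAP introduction: "we will calculate the difference in the detailed cost of the passive vs. active feedback versions of EQUIPPED". Protocol 2.3 wants labour cost to include planning and training "as well as the variable cost of delivering the intervention to each provider".

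For measuring time, Protocol 2.3 names one tool: "We have developed a log sheet with instructions that can be used by a sample of providers", who are to "log their activity time for patients in a given project over the course of a one-week period". SAP section 2 (Aim 3) repeats it: "to log their activity time for patients in a given project over the course of a one week period". Protocol 4.4.1, on paper records, confirms its role: "cost data will be calculated by using a log sheet with instructions". There the site champion appears as the person who collects the sheets. SAP section 5 (Aim 3) bases the analysis on whatever logs facilities return and averages time over logs and facilities, without saying that this is done separately by arm.

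The extra activity in the active arm is described elsewhere. Protocol 1.4.2 states: "The initial individual feedback session will be provided in-person to all staff providers (physician, APRN, PA"), and puts a session at about 15 minutes. Protocol 1.5.1, Stage 3, adds "ongoing monthly 1:1 feedback to outlier PIM prescribers in the ED at the site" over the one-year feedback period. Stage 2 adds champion coaching and a detailing module for active sites around launch.

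**The concern.** An active-minus-passive cost difference is only as good as the measurement of what differs between the arms. Much of that is short, infrequent staff-to-staff contact: once per provider near launch, then once a month for a subset. A one-week window suits tasks that recur every week. It suits these sessions poorly, because most weeks in any one provider's year contain none. The log is also worded in terms of time spent on patients, which does not obviously invite entries for a conversation between colleagues.

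Aim 3 has a practical purpose. Protocol 1.3 already calls in-person detailing the more resource-intensive approach. Protocol 2.3 says that earlier quality-improvement spending, an average of $50,000 per site, cannot be broken down, and that cost bears on whether the programme can be spread and sustained. If the detailing component is estimated near zero in one site and many times too high in another, the aim will not inform that decision.

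**Working it through.** The documents give no expected hours, number of logs or precision for Aim 3, so there is no planned figure to reproduce. The check uses the frequencies they do state.

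**Inputs from the documents**
- Session length: about 15 minutes = 0.25 h (Protocol 1.4.2).
- One initial session per staff provider (Protocol 1.4.2); monthly sessions for outliers (Protocol 1.5.1, Stage 3).
- Delivery period: one year, taken as 52 weeks.

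**Assumptions, because the documents are silent**
- One logged week is multiplied by 52.
- For the site illustration: N = 10 to 40 ED providers, with a share f = 10% to 30% classed as outliers. All initial sessions fall in one launch week, and each monthly round falls in one separate week.

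**Step 1: chance that a random week contains a given provider's session**
- Monthly session: 12/52 = 23.1%.
- One-off session: 1/52 = 1.9%.
- With 10 logs in independent random weeks, the chance that none contains a one-off session is (51/52)^10 = 82%. The chance that none contains a monthly session is (40/52)^10 = 7%, even if all 10 loggers are outliers.

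**Step 2: one outlier provider's monthly sessions**
- True time: 12 × 0.25 = 3 h a year.
- Logged week × 52: 0 h with probability 77%, or 0.25 × 52 = 13 h with probability 23%.
- Expected value: (12/52) × 13 = 3 h, so there is no bias if the week is random.
- Coefficient of variation for one log: √((1 − p)/p) with p = 12/52, i.e. √(40/12) = 183%.
- For the one-off session the expected value is also right, (1/52) × 13 = 0.25 h, but the coefficient of variation is √51 = 714%.

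**Step 3: detailer time at one active site, with N = 20 and f = 20%**
- Initial sessions: 20 × 0.25 = 5 h. Monthly round: 4 × 0.25 = 1 h. True year: 5 + 12 × 1 = 17 h.
- Log in launch week: 5 × 52 = 260 h, which is 260/17 = 15.3 times too high.
- Log in a monthly-round week: 1 × 52 = 52 h, or 52/17 = 3.1 times too high.
- Log in any of the other 52 − 13 = 39 weeks (75%): 0 h.
- Mean over a random week: (260 + 12 × 52)/52 = 17 h, again unbiased.
- Variance: (243² + 12 × 35² + 39 × 17²)/52 = 1,635, so the SD is 40.4 h. The coefficient of variation is 40.4/17 = 238% for one site and 238/√4 = 119% for the mean of four active sites.

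**Step 4: range over the assumed N and f**
- True detailer time, 0.25N + 3Nf: from 5.5 h (N = 10, f = 10%) to 46 h (N = 40, f = 30%) per site-year. Double this if the recipient's time is also costed.
- Launch-week ratio: 11.3 to 23.6. Monthly-week ratio: 2.4 to 3.4.
- If the week is not scaled at all, it shows 22% to 45% of the true hours (launch), 5% to 7% (monthly round) or none.

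**The case against.** A reader might infer that a one-week log cannot capture detailing at all, or that the cost difference is bound to be wrong in a known direction. The documents do not support either reading, for these reasons.

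- They do not say that the log is kept once, that its week is arbitrary, or that it is multiplied by 52. Timing it to launch or to a monthly round is not excluded. The sheet comes with instructions that are not reproduced and may settle some of this.
- Random weeks scaled to a year are unbiased, as Steps 2 and 3 show. The problem there is precision, which averaging over logs and facilities eases somewhat.
- The 23% and 2% describe one recipient. A champion or clinical partner sees many providers. In the Step 3 site, 4 × 12 = 48 monthly sessions spread evenly would put 48/52 = 0.9 in an average week, so the all-or-nothing pattern does not carry over to the person delivering them.
- Protocol 2.3 speaks of labour per task. The log might supply only minutes per task, with frequency taken from the design.
- The arms also differ in coaching, the extra training module, local consultation and on-screen alerts (Protocol 1.4.2 and 1.5.1, Stage 2), so detailing sessions are not the whole contrast.
- Protocol 2.3 allows the costing plan to be adjusted.

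All of this counts against a claim of certain failure. What it leaves standing is that no log week, repetition, logger or scaling rule is written down. No other time source is named, and nothing provides for counting the outlier sessions actually held. The champion is named as collector of the sheets, not as someone who keeps one.

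**Conclusion.** The point holds as a mismatch between the named instrument and an intermittent activity, not as proof of bias. As written, the 1:1 detailing time may be missed or over-scaled, and the labour difference between arms would be very imprecise. On the ×52 assumption, a provider's true 3 h a year is recorded as 0 or 13 h. On the further assumptions of Step 3, the four-site mean of detailer time has a coefficient of variation of about 119%. If all logs fell in a launch week or a quiet week, the estimate would be off by a factor of 11 to 24, or would be zero. Those site figures rest on assumed provider numbers, outlier shares and clustering of sessions, and would be milder if the person delivering the sessions logs and spreads them out.

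If log times were averaged over both arms together, the contrast would also be diluted. The SAP does not say that this will happen, only that averaging runs over logs and facilities.

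Aim 3 is a secondary costing aim. The primary PIM analysis does not use the logs and is unaffected. The change is worth making because it is cheap and gives a direct count of the activity that Aim 3 has to price.

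**What to change.** - Keep the one-week log for tasks that recur weekly, and state which week, who completes it, whether it is repeated, and how it is scaled to the year.
- Add two fields to the bi-monthly site report already planned (Protocol 2.2.1, step 4; SAP section 2, Aim 2, step 4): number of 1:1 sessions held and total minutes since the last report. Start with the launch period so that the initial sessions are included.
- Cost detailing as session minutes × wage, for both the person giving feedback and the provider receiving it. State the wage source: Protocol 2.3 and SAP section 2 use each provider's own rate, while SAP sections 5 and 8 use general salary information by position.
- Cost training and coaching once, from the scheduled calls and the training teleconference, not from the weekly log.
- State in SAP section 5 that log times are averaged within arm.

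The cost is two fields in an existing report and a few minutes of champion time every two months, with no extra staff. Minutes reported over two months carry some recall error. The session count should suffer less, and at about 15 minutes a session it gives a check on the reported total.
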